## 7. Risks and Discomforts

Patients will be informed that the foreseeable physical risks from this research study are minimal. They will be informed that there is some risk of breach of privacy/confidentiality associated with the use of written communication (e.g., emailing, text messages) and audio recording software. They will also be informed of the unlikely situation that they might feel uncomfortable with the topics discussed within the group, and they can alert the group leader who will provide help, as needed. The group leaders are experienced clinical psychologists who have specific expertise with chronic pain in adults. They will also be informed that they may feel uncomfortable completing various psychological questionnaires and that they may find it time-consuming to participate in weekly 60-minute groups.

In the unlikely event that a participant is determined to be in distress or actively suicidal and at risk for self-harm during any study procedure, we will use a standardized protocol for assessing and monitoring risk developed by [name] that has been successfully used in other remote trials. In this protocol, the research assistant would contact the MPI ([name]) and the appropriate clinical intervention would be executed. In case we are unable to contact the participant we will contact their safety contacts (see Potential Risks to participant section). In case suicidality is determined during the intervention or control sessions, the study clinicians will perform safety procedures in real time and immediately contact the MPIs. Further, we set serious mental illness and current suicidal ideation as exclusion criteria to further reduce the chance that enrolled participants would express harm towards themselves or others at any point during the study.

Direct adverse events from increasing walking are not expected. The increase in activity will be safe, quota-based and gradual, contingent upon meeting step count criteria in the previous week. All study staff have been trained in responsible conduct of research. Adverse events during the study will be tracked as part of the daily adherence/home practice log. Specifically, participants will be asked if they experienced any negative outcomes because of becoming more physically active during that day. Any participants reporting adverse events will be immediately contacted and, if necessary, assessed by the study clinician before being referred for appropriate care as needed.

As mentioned above, we will be using secure email to communicate with participants. All email communication with participants will be encrypted using the send secure function. To further protect participants' confidentiality, we will discourage participants from communicating about medical issues by non-secure email.

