The *GetActive-Fitbit* program is a group mind-body program developed iteratively from the Relaxation Response Resiliency Program (3RP) that incorporates additional cognitive behavioral and physical restoration skills (e.g., quota-based pacing) to help individuals increase self-reported, performance-based, and objectively measured (step count) physical function. Participants randomly assigned to this intervention condition will receive daily text/email reminders to practice program skills, record their walking, and record their skills practice via methods such as Twilio, if they consent to receive text reminders. A health education program (“Healthy Living for Pain”) will serve as the comparison condition for this aim of the study and will teach participants about health topics such as sleep, nutrition, and exercise. Participants randomly assigned to this comparison condition will receive journaling homework with daily text/email reminders. Participants will be given the option to share a copy of their journal with the study clinician throughout the program.

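### The only adverse event question specified is limited to harms participants attribute to being more active that day, and none is listed at post-test or 6 months, so the per-arm summary may miss other non-serious events

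*Combined protocol and SAP*

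**What the plan says.** Section 7 (Risks and Discomforts) sets the collection rule: "Adverse events during the study will be tracked as part of the daily adherence/home practice log". It then specifies the question: "participants will be asked if they experienced any negative outcomes because of becoming more physically active during that day". Follow-up of a report is also given: "Any participants reporting adverse events will be immediately contacted and, if necessary, assessed by the study clinician".

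The same section has a procedure for distress and suicidality that applies during any study procedure. For group sessions it names both arms: "In case suicidality is determined during the intervention or control sessions, the study clinicians will perform safety procedures in real time".

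Section 6 (Study Procedures) lists the measures for both arms at each time point and summarizes the visits in Table 1. On daily activity, GetActive-Fitbit participants "will receive daily text/email reminders to practice program skills, record their walking, and record their skills practice". For the other arm: "Participants randomly assigned to this comparison condition will receive journaling homework with daily text/email reminders".

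Section 10.1 says events may come to light through participants, the research team, clinicians or health records. It requires a summary for the safety committee, each year and at the end, by randomized group. That summary covers how many events and of what type, how severe, when they occurred, and whether they were related to the study.

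**The concern.** The log question makes the participant decide on cause before anything is recorded. The section 10.1 summary needs the opposite order: collect events, then judge relatedness. A participant who does not link a problem to activity has no reason to enter it, and nobody on the study side can then assess it.

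The question also fits poorly with the risks the protocol describes. Section 7 does not expect direct adverse events from more walking. The discomforts it does disclose concern privacy, group topics, questionnaires and time. The one specified question asks about the former and not the latter.

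At stake are the completeness of the per-arm summary and the comparability of its two columns, mainly for non-serious events. Serious events have expedited review once identified. Aim 3 is meant to optimize procedures for the later efficacy trial, so a collection gap is cheaper to close now than there.

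**Working it through.** The plan gives no adverse event figure to reproduce. The check is a count of listed items and a comparison of the routes by which an event could be recorded.

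**1. Scheduled measures (section 6).** The list has 16 entries: Demographics, Treatments, PEG-3, WHODAS and 6MWT (5), then ActiGraph, PROMIS depression, PROMIS anxiety, PCS, TSK, MOCS, CAMS, MGIC, CEQ, CSQ-3 and Fitbit Use (11).
- Post-test: 16 − 2 (Demographics, Fitbit Use) = 14.
- 6 months: 16 − 4 (Demographics, MGIC, CEQ, CSQ-3) = 12, or 11 for controls, who have no Fitbit Use item.
- Adverse event items: 0 at each. Table 1 adds none.

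**2. Routes side by side.**

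| Route | Arms | Needs self-attribution to activity? | Standard adverse event question on a schedule? |
|---|---|---|---|
| Daily log (section 7) | Not stated | Yes | Yes, daily; end not stated |
| PEG-3, WHODAS, PROMIS (section 6) | Both | No | No; scheduled scores of pain, disability and mood |
| Treatments (section 6) | Both | Content not described | Not shown; collected at post-test and follow-up |
| Distress and suicidality procedure (section 7) | Both | No | No; a response once risk is noticed |
| Participants, staff, clinicians, records (section 10.1) | No arm limit | No | No; no question or schedule given |

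Only the first row is an adverse event question, and it is the only row known to carry the attribution limit.

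**3. One event traced through.** Take a new, non-serious health problem that the participant does not connect with activity. The log question does not ask for it. A questionnaire score may move, but a score does not record an event with a type, a date and a relatedness judgement. The event reaches the summary only if the participant mentions it, someone notices it, or a record is reviewed.

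**4. Comparability of arms.** Daily recording of walking and practice is described only for GetActive-Fitbit; controls keep a journal, and sharing it is optional. The protocol does not say whether controls complete the log. If they do not, the specified question exists in one arm only. If they do, it may still apply to them, because the control program "will teach participants about health topics such as sleep, nutrition, and exercise". Neither the direction nor the size of any difference follows from this.

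**5. Duration of the log.** The end is not stated. Taking 6 months as about 26 weeks, the span from program start to last visit is 10 + 26 = 36 weeks. If the log stopped with the program, 26/36 = 72% of that span would have no specified adverse event question. If it ran to 6 months, the figure would be 0%. The text does not settle which, so this range only shows why the end date should be stated.

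**The case against.** The strongest reply is that collection is broader than the log. PEG-3, WHODAS and the PROMIS depression and anxiety scales ask both arms about plausible harms, on schedule and with no attribution filter. Treatments may pick up new care. The distress procedure covers the assessments as well as the sessions. Both arms meet a clinical psychologist weekly for 10 weeks, and section 10.1 accepts events from any source. For a study the protocol calls low risk, one targeted question plus passive reporting can be defended as proportionate. The assessment checklists mentioned in section 9 and the operating procedures mentioned in section 10 might also contain a prompt.

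Much of this stands, and it rules out several stronger readings that a reader might infer:
- That the log is the only route. Section 10.1 says otherwise.
- That harms unrelated to activity are never asked about. Worsening pain, disability and mood are measured.
- That control-arm events are under-recorded, or that one arm will look safer. The documents do not say who completes the log.
- That 72% of follow-up is uncovered. This rests wholly on an assumed end date, and section 7 speaks of tracking during the study.

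What the reply does not supply is a standard adverse event enquiry. The scales measure symptoms, the distress procedure is a response, and the section 10.1 routes depend on someone volunteering or noticing. A prompt that may sit in procedures outside the protocol cannot be credited to it.

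**Conclusion.** The point holds in limited form. The one adverse event question specified filters reports by the participant's own view of cause, and no adverse event item is listed at post-test or 6 months. The per-arm summary may therefore miss non-serious events not self-attributed to activity. It may also not be comparable between arms if only GetActive-Fitbit participants complete the log.

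The countable part is 0 of 16 listed measures. No number of missed events and no between-arm ratio can be derived, and none is claimed. No feasibility benchmark or planned test depends on this, and section 10.1 plans a descriptive summary. Severity is minor to moderate. The conclusion assumes that the section 6 list and Table 1 are the full assessment content, and that no adverse event prompt exists in operating procedures or checklists that the protocol does not describe.

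**What to change.** 1. Add one identical, attribution-free question for both arms at the existing post-test and 6-month assessments, for example: *any new or worsened health problem since the last assessment?* Judge relatedness afterwards.
2. State which arms complete the daily log and when it ends. If it is kept in both arms, remove the attribution wording.
3. In the per-arm summary, base the comparison on the common question and list log-reported and passively identified events separately.

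Weekly prompts at the sessions are optional. In a chronic pain sample they would also pick up ordinary fluctuation, and the defect does not require them. The check-in message between post-test and follow-up is a poor vehicle without a secure reply route, because section 7 says "we will discourage participants from communicating about medical issues by non-secure email".

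**Cost.** With 120 participants, two contacts give at most 2 × 120 = 240 answers. If retention only just meets the benchmarks (80% and 70%), the number is 96 + 84 = 180. For comparison, asking at all 10 sessions as well would give up to 12 × 120 = 1,440. The main downside is some additional minor events to record, classify and follow up, including the contact that section 7 requires for anyone who reports an adverse event. The rest is protocol wording.

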## **8. Benefits**

We expect many benefits from study participations among individuals in *GetActive-Fitbit* including improvement in physical (self-report, performance and objective) and emotional (depression and anxiety) function, increased coping ability, and decreases catastrophizing, fear of pain, and pain intensity. All participants are expected to benefit from the support of the therapist and group members. The potential benefits from this study far outweigh the potential risks. The data collected as part of this study may ultimately help researchers and clinicians better care for patients with chronic pain.

## **9. Statistical Analysis**

We plan to enroll N=120 participants across sites, with 40 participants recruited per site. We believe that this sample size is appropriate for a feasibility trial, including similar proposals previously funded NCCIH (e.g., 1U01AT010462). The proposed sample provides good power to achieve our multisite fidelity and feasibility benchmarks. Specifically, if 90 participants are enrolled, the study will have an 80% probability of meeting all seven Aim 2 feasibility benchmarks if the expected proportion of participants enrolling, completing at least 7 of 10 sessions, rating the program as credible and satisfactory, and completing post-treatment follow-up is at least 89% and if the expected proportion of protocol checklists deemed accurate is at least 95%. Moreover, the planned sample size will provide adequate precision for estimating fidelity and feasibility benchmarks.

### **Statistical analyses:**

First, we will report:

- percent eligible sedentary chronic pain patients who enroll after being determined eligible during screening (benchmark  $\geq 80\%$  AND 34/90 racial and ethnic minorities).

- Total duration of recruitment in months overall and at each site.
- Percent of patients who attend  $\geq 7/10$  sessions for each program (benchmark is 80%).
- Percent patients with credibility scores higher than the scale's mid point (Credibility and Expectancy scale; benchmark is 80%)
- Percent patients with satisfaction scores higher than the scale's mid point (Client Satisfaction scale; benchmark is 80%)
- Percent patients who complete post-treatment (benchmark is 80%) and 6 months follow up (benchmark is 70%) including self-report, performance based and Actigraph valid data.
- Percent accuracy of standardized protocol checklists for all assessments (benchmark is 90% accuracy).
- We will also report additional information necessary to complete the CONSORT diagram.

Next, we will use Fisher's exact tests to make comparisons of number of people meeting each benchmark across sites and between the intervention arms, while also plotting performance metrics across sites to account and assess for trends in differences due to the low statistical power.

Estimates of variance components required for design of a future efficacy trial will be obtained from preliminary analysis of outcome report, performance based, and objective/ambulatory measurements in mixed model repeated-measures analyses.

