**Summary of significance of the proposed NCCIH R01:** Chronic pain is a serious public health concern. Improving physical function is a top concern of people with chronic pain. Prior treatments are associated with only small improvement in physical function which tend to fade over time. No prior clinical trials in chronic pain have followed IMMPACT and ICF recommendations of assessing and addressing physical function comprehensively (e.g., self-report, performance based and objective). **Improving all aspects of physical function is imperative if we are to decrease the medical and economic burden of chronic pain and improve the lives of individuals with chronic pain (e.g., whole person).** We demonstrated that *GetActive-Fitbit* met or exceeded a-priori set feasibility benchmarks and was associated with improvements in comprehensive physical function among sedentary (5,000 steps/day) patients with chronic pain. Before conducting a multisite efficacy trial to demonstrate the efficacy of *GetActive-Fitbit*, we must demonstrate fidelity, feasibility/acceptability benchmarks, and refine our protocols in order to move from a local/single-site to a multi-site randomized controlled trial. Multiple sites allow for strong generalizability, and are necessary to generate a rate of recruitment for a targeted sample that will permit timely enrollment, long-term follow up, and evaluation of treatment mediators and moderators. Further, the multi-site feasibility testing allows us to correct limitations of our prior single-site study including recruitment of

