racially and ethnically diverse populations, accurate recruitment of the population of interest (chronic pain individuals who take less than 5,000 steps/day) and determining ability to follow-up participants after program completion in order to understand sustainability of improvements. We will also be able to further optimize the protocol and explore systemic barriers (through focus groups with staff) to enhance the rigor and success of the future efficacy testing. This project directly fits the NCCIH priority areas and 2021-2025 strategic plan of: 1) advancing research on the whole person (e.g., we are focused on improving comprehensive physical function - self-reported, performance based and step-count linked to valued activities, and emotional function); 2) integrating complementary and conventional care (e.g., we are recruiting patients who seek conventional medical care in pain clinics and integrating a mind-body activity within their care); 3) improving health in minorities and eliminating health disparities (e.g., we are specifically focused on recruiting a diverse sample of >38% racial and ethnic minorities); and 4) utilizing complementary and integrative management of pain. This project directly aligns with the NCCIH R01 PAR-21-241 to establish multi-site fidelity and feasibility benchmarks through a non-efficacy RCT. There is an opportunity for a patient centered paradigm shift in how chronic pain is currently treated in pain clinics, with important implications for improving physical function among this high-need population.

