## 2. Specific Aims and Objectives

**Aim 1:** To test multisite fidelity of training and implementation of *GetActive-Fitbit* vs *HEP*, among adults with heterogeneous, non-malignant, musculoskeletal chronic pain.

**Hypothesis:** We hypothesize that study clinicians can be trained consistently and competently across sites to achieve implementation of the 2 programs with high adherence and competence based on a-priori set benchmarks.

**Aim 2:** To evaluate multisite feasibility benchmarks including ability to recruit sedentary chronic pain patients and racial and ethnic minorities for a protocol involving randomization to *GetActive-Fitbit* versus *HEP* with post-program and 6 months follow up.

**Hypothesis:** We hypothesize that we will meet a-priori set feasibility benchmarks including ability to recruit and retain racial and ethnic minorities through a 6-months follow-up (38% minorities).

**Aim 3:** To optimize our fidelity and study implementation protocol procedures in preparation for a future fully powered multisite efficacy RCT through the UH3/UG3 mechanism (PAR-21-243).

**Hypothesis:** We expect that we will successfully refine training, implementation and procedures using an iterative approach with separate focus groups with patients and staff, and within and cross-site meetings.

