## **Inclusion/Exclusion Criteria**

### **Inclusion Criteria**

1. Male and female outpatients, age 18 years or older
2. Fluent in English
3. Have nonmalignant chronic musculoskeletal pain for more than 3 months
4. Able to perform a 6-minute walk test (6MWT)
5. Owns a smartphone with Bluetooth 4.0 or computer
6. Willingness and ability to participate in one of the 2 programs and to comply with the requirements of the study protocol.
7. Free of concurrent psychotropic medication for at least 2 weeks prior to initiation of treatment, OR stable on current medication for a minimum of 6 weeks and willing to maintain a stable dose

8. Low-level of activity (must meet 2/3 criteria; if difficult to assess, recruiter may ask participant to report their recent step data from their smartphone to better understand their activity level)
  - a. Sitting for more than 8 hours/day per self-report
  - b. Exercising for fewer than 3 days/week (30+min of exercise constitutes an “exercise day”) per self-report
  - c. Walking for fewer than 7 days/week (30+min of walking constitutes a “walking day”) per self-report

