All participants will wear the ActiGraph wGT3X-BT devices to measure step-count at baseline, post-intervention, and 6-month follow-up assessments. All participants will be instructed on ActiGraph maintenance using standard operating procedures used in a prior feasibility trial at MGH. Participants will return the ActiGraph watches after the assessments, provided they have logged seven consecutive days of valid data. Participants with missing data will be instructed to continue wearing the device until seven days have been reached. The RA will provide participants with ActiGraphs either in-person or via mail, and participants will be asked to return their devices during in-person assessments, during sessions, or via mail with a prepaid postage envelope. The RA will remotely monitor ActiGraph adherence using CentrePoint Sync. For participants in the *GetActive-Fitbit* condition, participants will be asked to wear a Fitbit Inspire 3 for the duration of the program and sync the Fitbit to a Fitbit application on their smartphone. Using the Fitbit steps, the RA will determine a new step count goal weekly based on whether the *GetActive-Fitbit* participant met their step goal in the prior week. If a participant met their step-count goal, they will increase their steps by 10%. If they did not meet the goal, they will continue with the same goal. If they do not meet the goal for 2 consecutive weeks, their goal will be increased by 10% of the average step count they had accomplished the week prior. Study clinicians may also conduct independent check-ins with participants who do not meet their goal to ensure barriers are known. The standard baseline goal for all participants randomized to the *GetActive-Fitbit* condition is that they experience a 1,000 step increase by the end of the program, though this will be variable depending on participant ability.

The following measures will be administered at all timepoints, to participants in both study arms, unless otherwise stated. The measures assess physical and emotional function, behavior, medical symptoms, and coping strategies with pain. These measures will be administered on hospital-owned encrypted devices or paper and pencil, depending on participant comfort, and should take about 30 minutes to complete.

Demographics (baseline only)

Treatments (post-tests and follow-up only)

Pain, Enjoyment of Life and General Activity scale (PEG-3)

WHO Disability Assessment Scale (WHODAS)

6 Minute Walk Test (6MWT)

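### The plan's only sedentary-recruitment measure is uptake among people already screened eligible, so it cannot show whether enrollees fit the under-5,000-steps/day population named in the Background

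*Combined protocol and SAP*

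**What the plan says.** All references are to the combined protocol and SAP.

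- **Section 1, Background and Significance.** Multisite testing "allows us to correct limitations of our prior single-site study". One limitation listed is "accurate recruitment of the population of interest (chronic pain individuals who take less than 5,000 steps/day". The same section elsewhere ties the word sedentary to 5,000 steps a day.
- **Section 2, Specific Aims.** The Aim 2 benchmarks include "ability to recruit sedentary chronic pain patients". No step count is given there.
- **Section 4, Inclusion Criteria, item 8.** Low activity is judged on self-reported sitting, exercise and walking: "must meet 2/3 criteria; if difficult to assess, recruiter may ask participant to report their recent step data from their smartphone". The walking item is "Walking for fewer than 7 days/week", where a walking day means at least 30 minutes. No step threshold appears. Section 5 confirms that eligibility is assessed by self-report.
- **Section 6, Study Procedures.** "All participants will wear the ActiGraph wGT3X-BT devices to measure step-count at baseline" and at both later assessments. Devices are returned "provided they have logged seven consecutive days of valid data"; people with missing data keep wearing them until seven days are reached.
- **Section 9, Statistical analyses.** The only item that mentions sedentary patients is "percent eligible sedentary chronic pain patients who enroll after being determined eligible during screening". Its benchmark is at least 80%, with a composition target of 34/90 that concerns race and ethnicity only.

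**The concern.** The document uses two definitions of the target population and does not connect them. The Background uses a step count; the inclusion criteria use a self-report rule. The Section 9 measure takes people who passed the self-report rule as its denominator, so it describes willingness to enroll. It carries no information on who those people are in terms of steps.

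This matters because the study's product is a protocol for a later efficacy trial. If Section 9 is followed as written, high uptake could be reported as success in recruiting sedentary patients while the limitation named in Section 1 stays unexamined. The same self-report screen could then be carried into the efficacy trial without evidence on whether it finds the stated population.

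**Working it through.** The plan states no expected or required share of enrollees below 5,000 steps/day, so there is no figure to reproduce. The check compares the passages and then asks what precision the missing estimate would have.

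**Step 1. Does the screen imply fewer than 5,000 steps/day?** Item 8 requires two of: (a) sitting over 8 hours a day; (b) fewer than 3 exercise days a week; (c) fewer than 7 walking days a week.

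| Person | a | b | c | Eligible on item 8? |
|---|---|---|---|---|
| Sits over 8 h, exercises 7 days, walks 30+ min on 6 days | met | not met | met | yes |
| Exercises 2 days, walks 30+ min on 6 days | any | met | met | yes |

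The second row assumes that walking is not counted as exercise; the first does not need that assumption. Step count plays no part in either result. The examples show only that the rule has no step limit. The documents do not convert minutes of walking to steps, so they do not show that these people exceed 5,000.

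**Step 2. Does the uptake benchmark depend on steps?**

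Uptake = (number enrolled) / (number found eligible at screening).

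Neither count involves steps, so the result is the same at any step distribution. For illustration, treat 90 as the number found eligible and take the 89% expected rate from Section 9. The chance of meeting 80% is then P(X ≥ 72), with X binomial (90, 0.89), which is 99.6%. That holds whatever share of enrollees walks fewer than 5,000 steps.

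**Step 3. Does another listed analysis fill the gap?** Section 9 uses ActiGraph data in two places. One is completeness at post-treatment and at 6 months. The other is the mixed models, whose stated purpose is variance components. The CONSORT item concerns the diagram of participant flow. None of these gives a share below 5,000.

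**Step 4. How precise would the missing estimate be?** Inputs: 120 planned, 40 per site (Section 9). The share is an assumption, varied from 50% to 90%. The exact (Clopper-Pearson) 95% limits for x out of n are:

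- lower: 0.025 quantile of Beta(x, n − x + 1)
- upper: 0.975 quantile of Beta(x + 1, n − x)

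| x/n | Share | Exact 95% CI |
|---|---|---|
| 60/120 | 50% | 40.7–59.3% |
| 72/120 | 60% | 50.7–68.8% |
| 84/120 | 70% | 61.0–78.0% |
| 96/120 | 80% | 71.7–86.7% |
| 108/120 | 90% | 83.2–94.7% |
| 63/90 (if only 90 give valid data) | 70% | 59.4–79.2% |
| 28/40 (one site) | 70% | 53.5–83.4% |

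At 84/120 the half-width is (78.0 − 61.0)/2 = 8.5 points. That is informative overall; a single site's figure is descriptive only.

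**Step 5. Which wear days count as baseline?** Table 1 places the baseline assessment about one week before the intervention. Section 6 lets wear continue until seven days are reached, and describes randomization as the next step after the baseline assessment. Make-up days could therefore fall after randomization or after the first session, when one arm is being encouraged to walk more. An estimate without a defined window could mix in such days.

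**The case against.** The strongest reply has four parts.

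1. **The data exist.** Everyone wears the ActiGraph at baseline, so the share can be tabulated at any time. This stands. A reader might infer that the study will be unable to say whether the pilot's limitation was corrected. The documents do not support that: the gap is in planned reporting, and nothing is lost beyond recovery.

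2. **The inclusion criteria may define sedentary for this trial.** The 5,000 figure appears only in the Background. Sections 2 and 9 use the word without a number, so in Section 9 it may simply mean having passed item 8. This also stands as a possible reading, and is why the definitions should be reconciled first. It does not remove the point, since Section 1 still promises accurate recruitment in terms of steps.

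3. **There is no evidence that the screen fails.** Correct. A reader might infer from the eligible examples that many enrollees will exceed 5,000 steps. The documents give neither a share nor a step conversion, so that does not follow.

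4. **The estimate will itself be biased.** Wearing a monitor may prompt people to walk more in the baseline week, which would understate the share below 5,000. Sections 3 and 6 include instructions meant to reduce this. The caveat belongs beside the estimate, but the documents give no basis for its size.

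**Conclusion.** The point holds as a gap in planned reporting that follows from two unreconciled definitions. The uptake rate cannot by itself support an Aim 2 statement about recruiting sedentary patients in the Section 1 sense, and no listed analysis supplies what is missing.

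The practical size is unknown because the true share below 5,000 is not given. At an assumed 70%, the estimate would have an exact 95% CI of 61.0% to 78.0%, if all 120 provide valid baseline data. That interval covers sampling error only, not reactivity or missing wear.

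No treatment comparison or test is invalidated. Nor does it follow that a pass mark for this share is required: a descriptive estimate with its interval is enough to inform the efficacy trial's design. The change is worth making before analysis because it bears on a stated aim and costs little.

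**What to change.** 1. **Reconcile the definitions.** State how the Section 1 step count and item 8 of the inclusion criteria relate, and whether *sedentary* in Sections 2 and 9 means having met item 8 or having a mean below 5,000 steps/day. Which definition governs is for the study team to decide.

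2. **Add one item to the Section 9 list.** Suggested wording: *number and percent of enrolled participants with valid baseline ActiGraph data whose mean is below 5,000 steps/day, overall with an exact 95% CI and by site descriptively; only wear days before the first group session are used, and any days after randomization are flagged; the number without valid baseline data is reported.*

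3. **Use it in the Aim 2 conclusion.** Base the statement on recruiting sedentary patients on this estimate together with the uptake rate. Note that baseline-week reactivity may understate the share.

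The cost is a clarifying sentence and one descriptive estimate from data already being collected. No benchmark, eligibility change, added data collection or change to the sample-size paragraph is needed. The downside is that the estimate may show the self-report screen missing the stated target, and reactivity may make the screen look worse than it is.
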